3.7 Interim Analyses

3.7.1 Efficacy Interim Analysis

An IA for testing the primary efficacy hypothesis will be conducted upon accrual of a total of 15 CMVi endpoint cases in the combined V160 3-dose and placebo regimens. Possible outcomes of this IA and consequent study pathways are as described below and shown in schematic form in [Figure 1](#).

1. ≥7 of 15 CMVi cases observed in the V160 3-dose arm
 - Study fails to demonstrate the primary efficacy hypothesis at the IA and has no chance of successfully demonstrating the primary efficacy hypothesis in a final analysis when a total of 24 CMVi cases are accrued in the combined V160 3-dose regimen and placebo groups.
 - eDMC may recommend the study to be terminated for futility.
2. (4, 5, or 6) of 15 CMVi cases observed in the V160 3-dose arm.

- Result of testing of the primary efficacy hypothesis is inconclusive.
 - Study fails to demonstrate the primary efficacy hypothesis at the IA but still has a chance of demonstrating the primary efficacy hypothesis in a final analysis when a total of 24 CMVi cases are accrued in the combined V160 3-dose regimen and placebo groups.
 - Study (which is still blinded) will continue until a total of 24 CMVi cases are accrued in the combined V160 3-dose regimen and placebo groups, at which time, the final testing of the primary efficacy hypothesis will be conducted.
3. ≤ 3 of 15 CMVi cases observed in the V160 3-dose arm
- Study successfully demonstrates the primary efficacy hypothesis.
 - The appropriate timing for the testing the secondary efficacy hypothesis is evaluated (see Section 10.6.1).

[figure not shown]

Figure 1 Plan for Testing the Primary and Secondary Efficacy Hypotheses

3.7.2 Safety Interim Analysis

At the time of IA for efficacy, the eDMC will also conduct a review of the cumulative study safety data recorded in the study database upon which the 15 CMVi cases was counted and confirmed to have been accumulated. No hypothesis relating to safety will be tested.

Summaries of safety parameters identified in Section 10.6.3 Statistical Methods for Safety Analyses, will be prepared for review by the eDMC.

3.8 Multiplicity

The overall 1-sided Type 1 error in testing the efficacy hypotheses is controlled to not exceed 2.5% based on gatekeeping procedure.

The primary efficacy hypothesis will be tested at an overall (over the IA and final analysis) 1-sided Type 1 error $<2.5\%$, as discussed in Section 3.9.1. The secondary efficacy hypothesis will be tested at 1-sided Type 1 error $\leq 2.5\%$ only if the primary efficacy hypothesis is successfully demonstrated, as discussed in Section 3.9.2. The primary efficacy hypothesis is a reasonable gatekeeper to the secondary efficacy hypothesis because if a V160 3-dose regimen with last dose at Month 6 is not efficacious, then a V160 2-dose regimen with last dose also at Month 6 is highly unlikely to be efficacious.

3.9 Sample Size and Power Calculations

3.9.1 Sample Size and Power for Efficacy Analyses

3.9.1.1 Sample Size and Power for Testing the Primary Efficacy Hypothesis

The power corresponding to the decision rule that will be implemented in testing the primary efficacy hypothesis is based on a fixed-event design. For testing the primary efficacy hypothesis, participants will be followed until 15 total CMVi cases in the combined V160 3-dose and placebo regimens have been accumulated, at which point, an IA will be conducted. If the testing of the primary efficacy hypothesis is inconclusive at the IA, follow-up will continue until 24 total CMVi cases have been observed in the combined V160 3-dose and placebo regimens. The decision rules to be implemented that will determine success or failure to demonstrate the primary efficacy hypothesis are as shown in [Figure 1](#) in Section 3.7 and in [Table 2](#). Corresponding to these decision rules, the study has $>90\%$ power to demonstrate that the efficacy of a V160 3-dose regimen compared to placebo to prevent CMVi is $>0\%$ if the underlying vaccine efficacy is $\geq 80\%$ at an overall one-sided Type 1 error equal to 2.3%. The operating characteristics of the decision rules with one IA and a final analysis if necessary are evaluated by a 5 million-replication simulation using SAS v9.4. In the simulation conducted, the underlying probability distribution of accumulation of CMVi cases in the V160 3-dose regimen conditional on the total cases in the combined V160 and placebo regimens is based on an exact method under a large sample Poisson distribution assumption proposed by Chan and Bohidar (1998) [1].

This study will randomize 700 participants into the V160 3-dose regimen and 700 into the placebo regimen. The 15 total CMVi cases in the combined V160 3-dose and placebo regimens are projected to be accumulated in ≈ 18 to 19 months under the following assumptions: 1) all 1,400 participants are enrolled within 18 months; 2) incidence of CMVi in the placebo group is 2% per year; 2) VE=85%, so that the incidence of CMVi in the V160 arm is 0.3% per year; 3) loss-to-follow-up is $\approx 5\%$ to 10% per year; and 4) participants ineligible for the PPE analysis is $\approx 2\%$ to 5% of participants randomized. Under the same assumptions, the total of 24 CMVi cases in the combined V160 3-dose and placebo regimens is projected to be accumulated in ≈ 3 years.

It is possible that at the time when CMVi cases are counted to determine whether a total of 15 cases have been accrued, the actual CMVi cases accumulated will already be greater than 15. In such an eventuality, the IA will be conducted based on the actual number of cases accrued (eg, 16, or 17, or some other count). [Table 2](#) also shows the operating characteristics of decision rules that will be used in the eventuality that the IA is conducted at a total case count greater than 15.

Table 2 Decision Rule and Corresponding Type 1 Error and Power for Testing the Primary Efficacy Hypothesis of VE >0% Against CMVi (3-Dose Regimen vs. Placebo)

| Total Cases Available at IA | Analysis Time Point | Total Cases to Accrue | Stop for Futility (Vacc Cases) | Case Split for Success (Vacc:Pbo) | VE (95% CI) ^a | Cumulative Type I Error ^b | True Vaccine Efficacy | | | | | |
|-----------------------------|---------------------|-----------------------|--------------------------------|-----------------------------------|--------------------------|--------------------------------------|-----------------------|-------|-------|-------|-------|-------|
| | | | | | | | 70% | 75% | 80% | 85% | 90% | 95% |
| | | | | | | | Cumulative Power | | | | | |
| 15 | IA | 15 | ≥7 | ≤3 : ≥12 | 75.0 (7.4, 95.5) | 1.8% | 53.2% | 64.8% | 76.8% | 87.8% | 95.9% | 99.5% |
| | Final† | 24 | ≥7 | ≤6 : ≥18 | 66.7 (12.3, 89.2) | 2.3% | 73.0% | 83.7% | 92.3% | 97.5% | 99.6% | 100% |
| 16 | IA | 16 | ≥8 | ≤3 : ≥13 | 76.9 (16.0, 95.8) | 1.1% | 47.7% | 59.9% | 72.9% | 85.4% | 94.9% | 99.4% |
| | Final† | 26 | ≥8 | ≤7 : ≥19 | 63.2 (8.5, 86.9) | 2.1% | 78.0% | 87.8% | 94.9% | 98.7% | 99.9% | 100% |
| 17 | IA | 17 | ≥8 | ≤3 : ≥14 | 78.6 (23.2, 96.1) | 0.6% | 42.4% | 54.9% | 68.9% | 82.8% | 93.8% | 99.3% |
| | Final† | 26 | ≥8 | ≤7 : ≥19 | 63.2 (8.5, 86.9) | 1.7% | 77.3% | 87.4% | 94.7% | 98.6% | 99.8% | 100% |
| 18 | IA | 18 | ≥8 | ≤4 : ≥14 | 71.4 (9.0, 93.2) | 1.6% | 59.6% | 71.6% | 83.2% | 92.5% | 98.1% | 99.9% |
| | Final† | 26 | ≥8 | ≤7 : ≥19 | 63.2 (8.5, 86.9) | 2.3% | 78.8% | 88.3% | 95.1% | 98.7% | 99.9% | 100% |
| 19 | IA | 19 | ≥8 | ≤4 : ≥15 | 73.3 (16.3, 93.6) | 1.0% | 54.5% | 67.3% | 80.1% | 90.9% | 97.5% | 99.8% |
| | Final† | 26 | ≥8 | ≤7 : ≥19 | 63.2 (8.5, 86.9) | 1.9% | 77.7% | 87.7% | 94.8% | 98.6% | 99.9% | 100% |
| 20 | IA | 20 | ≥8 | ≤5 : ≥15 | 66.7 (3.5, 90.5) | 2.1% | 69.4% | 80.4% | 89.8% | 96.3% | 99.3% | 100% |
| | Final† | 27 | ≥8 | ≤7 : ≥20 | 65.0 (13.8, 87.5) | 2.4% | 78.1% | 87.9% | 94.9% | 98.6% | 99.9% | 100% |
| 21 | IA | 21 | ≥9 | ≤5 : ≥16 | 68.8 (10.7, 91.0) | 1.3% | 64.8% | 76.9% | 87.6% | 95.3% | 99.1% | 100% |
| | Final† | 28 | ≥9 | ≤8 : ≥20 | 60.0 (5.2, 84.8) | 2.3% | 83.5% | 91.7% | 97.0% | 99.3% | 99.9% | 100% |
| 22 | IA | 22 | ≥9 | ≤5 : ≥17 | 70.6 (16.9, 91.5) | 0.9% | 60.2% | 73.3% | 85.3% | 94.2% | 98.8% | 100% |
| | Final† | 29 | ≥9 | ≤8 : ≥21 | 61.9 (10.5, 85.4) | 1.6% | 80.4% | 89.9% | 96.2% | 99.1% | 99.9% | 100% |

^a Upon completion of the analyses, a multiplicity-adjusted p-value and confidence interval will be calculated using the group-sequential methodology of Jennison and Turnbull (2000).
^b Type I error and power shown are cumulative over the IA and final analysis.
CI = Confidence interval; IA = Interim analysis; VE = Vaccine efficacy.

Final Testing of the Primary Efficacy Hypothesis

The eDMC conducted the IA on March 17, 2020 based on a total of 17 primary endpoint cases in the combined V160 3-dose and placebo groups. After the IA was conducted, the eDMC recommended the study to continue unchanged. This eDMC recommendation implies:

1. The study did not meet the futility criterion at the IA.
2. The testing of the efficacy hypotheses (or hypothesis if only the secondary efficacy hypothesis needs to be tested at a future time) is paused.
3. It is unknown to the V160-002 blinded study team whether:
 - i. The test of the primary efficacy hypothesis succeeded but there are not enough primary efficacy endpoint cases available in the combined V160 2-dose and placebo groups to test the secondary efficacy hypothesis (see Figure 1); OR
 - ii. The test of the primary efficacy hypothesis is inconclusive so that more cases of the primary efficacy endpoint in the combined V160 3-dose and placebo groups need to be accumulated (see Figure 1).

If the pause in efficacy hypotheses testing is due to 3.ii above, because the IA was conducted at 17 total cases of the primary endpoint in the combined V160 3-dose and placebo groups, then the final testing of the primary efficacy hypothesis will be conducted when at least 26 total cases of the primary endpoint have been accrued (see [Table 2](#)). In the event of over running the required 26 total cases of the primary endpoint in the combined V160 3-dose and placebo groups when the available efficacy endpoint cases are counted, [Table 3](#) provides the decision rules that will be applied at the final testing of the primary efficacy hypothesis (conditional on the IA being conducted at 17 total cases in the combined V160 3-dose and placebo groups).

Table 3 Decision Rule and Corresponding Type 1 Error and Power for Testing the Primary Efficacy Hypothesis of VE >0% Against CMVi, Conditional on the IA Being Conducted at 17 Total Cases (3-Dose Regimen vs. Placebo)

| Cases Available at Final Analysis | Analysis Time Point | Total Cases to Accrue | Stop for Futility (Vacc Cases) | Case Split for Success (Vacc:Pbo) | VE (95% CI) ^a | Cumulative Type I Error ^b | True Vaccine Efficacy | | | | | |
|-----------------------------------|---------------------|-----------------------|--------------------------------|-----------------------------------|--------------------------|--------------------------------------|-----------------------|-------|-------|-------|-------|-------|
| | | | | | | | 70% | 75% | 80% | 85% | 90% | 95% |
| | | | | | | | Cumulative Power | | | | | |
| 26 | IA | 17 | ≥8 ^c | ≤3 : ≥14 | 78.6 (23.2, 96.1) | 0.6% | 42.4% | 54.9% | 68.9% | 82.8% | 93.8% | 99.3% |
| | Final† | 26 | ≥8 | ≤7 : ≥19 | 63.2 (8.5, 86.9) | 1.7% | 77.3% | 87.4% | 94.7% | 98.6% | 99.8% | 100% |
| 27 | IA | 17 | — ^c | ≤3 : ≥14 | 78.6 (23.2, 96.1) | 0.6% | 42.4% | 54.9% | 68.9% | 82.8% | 93.8% | 99.3% |
| | Final† | 27 | ≥8 | ≤7 : ≥20 | 65.0 (13.8, 87.5) | 1.3% | 74.2% | 85.3% | 93.7% | 98.3% | 99.8% | 100% |
| 28 | IA | 17 | — ^c | ≤3 : ≥14 | 78.6 (23.2, 96.1) | 0.6% | 42.5% | 54.9% | 68.9% | 82.8% | 93.8% | 99.3% |
| | Final† | 28 | ≥9 | ≤8 : ≥20 | 60.0 (5.2, 84.8) | 2.1% | 82.7% | 91.3% | 96.8% | 99.3% | 99.9% | 100% |
| 29 | IA | 17 | — ^c | ≤3 : ≥14 | 78.6 (23.2, 96.1) | 0.6% | 42.4% | 54.9% | 68.9% | 82.8% | 93.8% | 99.3% |
| | Final† | 29 | ≥9 | ≤8 : ≥21 | 61.9 (10.5, 85.4) | 1.6% | 80.1% | 89.7% | 96.1% | 99.1% | 99.9% | 100% |
| 30 | IA | 17 | — ^c | ≤3 : ≥14 | 78.6 (23.2, 96.1) | 0.6% | 42.4% | 54.9% | 68.9% | 82.8% | 93.8% | 99.3% |
| | Final† | 30 | ≥10 | ≤9 : ≥21 | 57.1 (2.4, 82.7) | 2.4% | 87.1% | 94.1% | 98.1% | 99.7% | 100% | 100% |
| 31 | IA | 17 | — ^c | ≤3 : ≥14 | 78.6 (23.2, 96.1) | 0.6% | 42.4% | 54.9% | 68.9% | 82.8% | 93.8% | 99.3% |
| | Final† | 31 | ≥10 | ≤9 : ≥22 | 59.1 (7.6, 83.4) | 1.8% | 84.8% | 92.9% | 97.6% | 99.6% | 100% | 100% |
| 32 | IA | 17 | — ^c | ≤3 : ≥14 | 78.6 (23.2, 96.1) | 0.6% | 42.4% | 54.9% | 68.9% | 82.8% | 93.8% | 99.3% |
| | Final† | 32 | ≥10 | ≤9 : ≥23 | 60.9 (12.2, 84.1) | 1.4% | 82.5% | 91.5% | 97.1% | 99.4% | 100% | 100% |
| 33 | IA | 17 | — ^c | ≤3 : ≥14 | 78.6 (23.2, 96.1) | 0.6% | 42.4% | 54.9% | 68.9% | 82.8% | 93.8% | 99.3% |
| | Final† | 33 | ≥11 | ≤10 : ≥23 | 56.5 (5.0, 81.5) | 2.1% | 88.6% | 95.1% | 98.6% | 99.8% | 100% | 100% |
| 34 | IA | 17 | — ^c | ≤3 : ≥14 | 78.6 (23.2, 96.1) | 0.6% | 42.4% | 54.9% | 68.9% | 82.8% | 93.8% | 99.3% |
| | Final† | 34 | ≥11 | ≤10 : ≥24 | 58.3 (9.6, 82.2) | 1.6% | 86.6% | 94.1% | 98.2% | 99.7% | 100% | 100% |
| 35 | IA | 17 | — ^c | ≤3 : ≥14 | 78.6 (23.2, 96.1) | 0.6% | 42.4% | 54.9% | 68.9% | 82.8% | 93.8% | 99.3% |
| | Final† | 35 | ≥12 | ≤11 : ≥24 | 54.2 (2.8, 79.7) | 2.4% | 91.4% | 96.7% | 99.2% | 99.9% | 100% | 100% |

^a Upon completion of the analyses, a multiplicity-adjusted p-value and confidence interval will be calculated using the group-sequential methodology of Jennison and Turnbull (2000).

^b Type I error and power shown are cumulative over the IA and final analysis.

^c The IA was conducted at 17 total cases based on the plan that the final analysis, if needed, would be conducted at 26 total cases. For this plan, the futility criterion at the IA was occurrence of ≥8 cases in the V160 3-dose group. When the IA was conducted on March 17 2020, the futility criterion was not met. If the final analysis needs to be conducted and is conducted at a total of 27 or more cases, the futility criterion at the IA is no longer needed nor relevant since the IA has already been conducted.

CI = Confidence interval; IA = Interim analysis; VE = Vaccine efficacy.

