3.6.1 Statistical Methods for Efficacy Analyses

To address the primary and secondary efficacy hypotheses, one-sided tests of the null hypothesis that the vaccine efficacy is 0% versus the alternative that vaccine efficacy is >0% will be conducted separately for each of the primary and secondary hypotheses. Each of the primary and secondary efficacy hypotheses will be tested at one-sided $\alpha=0.025$ level (ie, 2.5% Type 1 error). Vaccine efficacy is defined as:

$$VE = 100\% * \{1 - (R_v/R_p)\}$$

where R_v and R_p are the incidence rates CMVi in the V160 dose regimen (3-dose for the primary efficacy hypothesis testing; 2-dose for the secondary efficacy hypothesis testing) and placebo groups, respectively. The incidence rate R_v is defined as $R_v = C_v/T_v$, where C_v = the count of CMVi cases in the vaccine group and T_v = total person-years of follow-up for efficacy in the vaccine group. The incidence rate R_p is defined similarly. The null hypothesis that vaccine is not efficacious (ie, $VE=0\%$) will be tested by constructing a $100*(1-\alpha)\%$ confidence interval (CI) for VE, denoted as (VE_L, VE_U) , based on study data at a particular analysis time point (eg, at IA or at final analysis). The statistical criterion for success with respect to the primary efficacy hypothesis (and likewise for the secondary efficacy hypothesis) will be met if $VE_L > 0\%$.

The $100*(1-\alpha)\%$ CI for VE, (VE_L, VE_U) , is constructed as follows. Under the assumption that R_v and R_p are the means of independent Poisson processes, and given that there is a total of $n = C_v + C_p$ efficacy endpoint cases observed in the combined V160 dose regimen and placebo groups, then the number of primary efficacy cases C_v in the V160 dose regimen group is distributed as Binomial(n, π), where the binomial probability π is defined as $\pi = T_v R_v / (T_v R_v + T_p R_p)$. The probability π is a person-years-adjusted estimate of the probability

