that a particular study participant who became a case of CMVi belongs to the V160 dose regimen group. The lower bound of the $100*(1-\alpha)$ % exact CI for the probability π is obtained by searching for the proportion π_L such that the probability of observing C_v or more efficacy endpoint cases out of n total efficacy cases is $\leq \alpha/2$. Similarly, the upper bound of the $100*(1-\alpha)$ % exact CI for the probability π is obtained by searching for the proportion π_U such that the probability of observing C_v or fewer efficacy endpoint cases out of n total efficacy cases is $\leq \alpha/2$ [1]. VE_L and VE_U are then calculated from π_L and π_U as follows:

$$VE_L = 100\% * \{1 - \pi_U (1+\theta)\} / (1 - \pi_U);$$
$$VE_U = 100\% * \{1 - \pi_L (1+\theta)\} / (1 - \pi_L);$$

where $\theta = T_p/T_v$ is the ratio of the total person-years of follow-up for efficacy in the placebo group over the V160 dose regimen group.

There is only one final analysis of the secondary efficacy endpoint. However, the testing of the secondary efficacy hypothesis may occur at the time of the IA or the final analysis of the primary efficacy hypothesis. The secondary efficacy hypothesis will only be tested if the primary efficacy hypothesis is successfully demonstrated. In addition, the secondary efficacy hypothesis will be tested contingent on accumulation of ≥ 15 total CMVi cases in the V160 2-dose and placebo regimens (see [Figure 1](#) in Section 3.7, and Section 3.9.2). Thus, the possible timing for testing the secondary hypothesis is as follows.

- If the primary hypothesis test is successful at the IA *and* there are ≥ 15 total CMVi cases in the V160 2-dose and placebo regimens at the time of IA, then the secondary efficacy hypothesis will be tested immediately after the testing of the primary efficacy hypothesis at the time of the IA.
- If the primary hypothesis test is successful at the IA and there are < 15 total CMVi cases in the V160 2-dose and placebo regimens at the time of IA, the secondary efficacy hypothesis will not be tested at the IA. In this case, follow-up will continue until at least 15 total CMVi cases in the V160 2-dose and placebo regimens groups are accrued. Upon accrual of ≥ 15 total CMVi cases in the V160 2-dose and placebo regimens, the secondary efficacy hypothesis will be tested.
- If the primary hypothesis test is not successful at the IA, the secondary efficacy hypothesis will not be tested at the time of the IA.

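### The sSAP gives two success rules, a person-time-adjusted limit and fixed case splits, without saying which governs; neither alone guarantees the 2.5% cap for the primary test

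*Combined protocol and SAP*

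**What the plan says.** Two success rules stand side by side in the sSAP, and the protocol has the same pair in 10.6.1 and in 10.7.1 and 10.9.1.

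- **Person-time rule (sSAP 3.6.1).** "The statistical criterion for success with respect to the primary efficacy hypothesis (and likewise for the secondary efficacy hypothesis) will be met if" the lower limit VE_L is above 0%. The limit comes from an exact conditional binomial interval and depends on θ, which "is the ratio of the total person-years of follow-up for efficacy in the placebo group over the V160 dose regimen group".
- **Case-split rule (sSAP 3.7.1, 3.9.1.1, 3.9.1.2).** Section 3.9.1.1 says "The decision rules to be implemented that will determine success or failure to demonstrate the primary efficacy hypothesis are as shown in" Figure 1 and Table 2. Section 3.7.1 attaches the outcome "Study successfully demonstrates the primary efficacy hypothesis" to 3 or fewer V160 cases out of 15, with no condition on person-time. Tables 3 and 4 are likewise presented as the rules to be applied if case totals overrun.

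On error control, section 3.8 states: "The overall 1-sided Type 1 error in testing the efficacy hypotheses is controlled to not exceed 2.5% based on gatekeeping procedure". On the state of the trial, 3.9.1.1 reports: "The eDMC conducted the IA on March 17, 2020 based on a total of 17 primary endpoint cases" in the 3-dose and placebo arms. The planned final primary test, if needed, is therefore at 26 cases, with Table 3 covering 26 to 35. Footnote a to Tables 2 and 3 promises a multiplicity-adjusted p-value and interval once the analyses are complete, but does not make them the decision rule.

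**The concern.** Under no efficacy, a case falls in the V160 arm with probability Tv/(Tv+Tp), where Tv and Tp are the person-years in the V160 and placebo arms. That is one half only if the arms have equal follow-up. A fixed split cannot respond if they do not: when V160 has less person-time, fewer V160 cases are expected even with a useless vaccine, and the same split is easier to meet. The 3.6.1 limit does respond, but it is a nominal 95% limit and takes no account of the error already spent at the interim.

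The two rules can therefore disagree on the same data, and they already differ at the interim that was held. At 17 cases and equal person-time, VE_L > 0% allows 4 V160 cases (lower limit 0.4% in Table 4), while Table 2 allows 3. What is at stake is the 2.5% claim in section 3.8 and a success decision that does not depend on which section the analyst reads.

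**Working it through.** **Inputs.** Splits, stated errors and limits from sSAP Tables 2-4; the cap from 3.8; the interim at 17 cases from 3.9.1.1; VE_L and θ = Tp/Tv from 3.6.1. Write r = Tv/Tp. The value of r is not in the documents, so it is varied as an assumption.

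**Formulas.** Given n cases, the V160 count is Binomial(n, π) with π = r(1−VE)/(r(1−VE)+1); under VE = 0, π = r/(1+r). Cumulative error with interim cut c1 of n1 and final cut c2 of n2:

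P(X1 ≤ c1) + Σ over x > c1 of P(X1 = x)·P(Binomial(n2−n1, π) ≤ c2−x).

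The 3.6.1 limit rearranges to VE_L = 1 − θ·πU/(1−πU), so VE_L > 0 exactly when r > πU/(1−πU).

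**Step 1: reproduce the plan at r = 1.** Planned 15/24 design (≤3, ≤6): interim 1.76%, cumulative 2.34%, power 92.3% at VE 80% (stated 1.8%, 2.3%, 92.3%). Actual 17/26 design (≤3, ≤7): interim 0.64%, cumulative 1.73% (stated 0.6%, 1.7%). Every design in Tables 2 and 3 and every error in Table 4 reproduces to within 0.1 point. The tabulated VE limits also reproduce with θ = 1: for 4 of 17, πU/(1−πU) = 0.996, so VE_L = 0.4%; for 7 of 26, 0.915 and 8.5%; for 9 of 30, 0.976 and 2.4%. The tables therefore assume equal person-time.

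**Step 2: if the splits govern.** Cumulative error for Table 3 rows (interim ≤3 of 17), and the V160 shortfall at which it reaches 2.5%:

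| Final cases (cut) | r = 1 | r = 0.97 | r = 0.95 | Shortfall reaching 2.5% |
|---|---|---|---|---|
| 26 (≤7) | 1.73% | 2.08% | 2.35% | 6.0% |
| 27 (≤7) | 1.32% | 1.60% | 1.81% | 10.1% |
| 28 (≤8) | 2.07% | 2.50% | 2.82% | 3.0% |
| 29 (≤8) | 1.57% | 1.90% | 2.16% | 7.3% |
| 30 (≤9) | 2.43% | 2.93% | 3.32% | 0.45% |
| 31 (≤9) | 1.83% | 2.22% | 2.53% | 4.8% |
| 32 (≤9) | 1.42% | 1.73% | 1.98% | 8.5% |
| 33 (≤10) | 2.11% | 2.57% | 2.93% | 2.6% |
| 34 (≤10) | 1.63% | 1.99% | 2.28% | 6.3% |
| 35 (≤11) | 2.40% | 2.93% | 3.35% | 0.6% |

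Over all rows the shortfall needed is 1.1-7.2% in Table 2, 0.45-10.1% in Table 3 and about 0.4-17% in Table 4. The tightest Table 4 row is 17 cases (≤4): at r = 0.995 the split declares success while VE_L = 1 − 0.996/0.995, which is below 0.

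**Step 3: if nominal VE_L > 0% governs.**
- Secondary, one look: the error stays at or below 2.5% at any r, because the interval uses the observed person-time.
- Primary, both looks at r = 1: the cuts become ≤4 of 17 and ≤7 of 26. The error is 2.45% at the interim plus 0.64% added at the final, 3.09% in all.
- Primary, interim cut kept at ≤3 of 17, final at 30 cases, r = 0.99: π = 0.99/1.99 = 0.4975. For 9 of 30, VE_L = 1 − 0.976/0.99 = 1.4%, so the criterion is met, yet the cumulative error is 2.59%. At 35 cases it is 2.57%.

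**The case against.** The strongest reply is that the plan already has a person-time-adjusted test. Section 3.6.1 prescribes it, the objectives repeat the lower-limit criterion, and the tables sit under a sample-size heading. This stands in part. A reader might infer that the plan has only fixed splits and no test using person-years; that is wrong, and if 3.6.1 governs, the secondary test needs no repair. But the wording of 3.9.1.1 makes the splits decide, and no passage resolves the conflict.

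Second, the row that matters is robust. The planned 17/26 design stays under the cap to a 6.0% shortfall, and its split agrees with VE_L > 0% to 8.5%. That also stands. The rows with under 1% slack, 30 and 35, need overruns of 4 and 9 cases.

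Third, a reader might infer that V160 recipients are likely to contribute less person-time, given the adjuvant's reactogenicity, a saline control and a per-protocol set requiring three in-window injections. The documents do not establish this. The Phase 1 remark in protocol 3.2.2.2 compares adjuvanted with unadjuvanted vaccine and gives no discontinuation data against saline. Section 3.9.1.1 assumes 2-5% ineligibility overall, not by arm. Chance imbalance is symmetric: if eligibility alone drives it, with 700 per arm, the SD of the relative difference is √(2q(1−q)·700)/(700(1−q)), or 0.8% at q = 2% and 1.2% at q = 5%. Averaged over that, no Table 3 row exceeds 2.44%. Only a systematic V160 shortfall breaks the cap.

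**Conclusion.** The point holds as a conflict between two unreconciled rules, with an unstated assumption of Tp/Tv = 1 behind the tables. Under the splits, the cap depends on each row's slack: 6.0% for 17/26, and as little as 0.45% in Table 3 and about 0.4% in Table 4. Under the nominal limit, the secondary is protected, but the primary can reach 3.1% at equal person-time if the limit is used at both looks, or 2.59% at 30 cases with 1% less V160 person-time and the interim cut kept at 3. That second excess comes from error spent at the interim, not from missing person-time adjustment.

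Two stronger readings should be resisted. The splits do not hold the cap only at equal person-time: they also hold it when V160 has more follow-up, or a shortfall within the row's slack. Nor do the documents show that the cap is breached in this trial, since actual person-time by arm, its direction and the final case total are not given. The calculation rests on the Poisson model of 3.6.1 and on assumed values of r.

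**What to change.** 1. State in 3.9.1 that the splits, errors and limits in Tables 2-4 are computed at Tp/Tv = 1, and name one governing rule for each hypothesis in 3.6.1, 3.7.1 and 3.9.1.
2. Primary final test, if still needed: the external statistician recomputes the critical count with null probability Tv/(Tv+Tp) from observed per-protocol person-years, keeping the completed interim cut (≤3 of 17), as the largest count with cumulative one-sided error of at most 2.5%. That count decides.
3. Secondary test: the 3.6.1 person-time-adjusted exact test (VE_L > 0%) decides, and the Table 4 splits are labelled illustrative.

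The cost is SAP wording and a few lines of code, before unblinding. The critical count usually falls by one when V160 person-time is short enough to matter, with some loss of power. At 17/26 with 7% less V160 person-time it is ≤6 instead of ≤7 (error 1.41% instead of 2.66%), with power 91.1% at VE 80%. At 17/30 with 1% less it is ≤8 instead of ≤9 (1.31% instead of 2.59%), with power 95.5%. At a 10% shortfall the 35-case row loses two (≤9 instead of ≤11).

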It is possible that at the time when CMVi cases are counted to determine whether a total of 15 cases have been accrued, the actual CMVi cases accumulated will already be greater than 15. In such an eventuality, the IA will be conducted based on the actual number of cases accrued (eg, 16, or 17, or some other count). The operating characteristics shown in [Table 6](#) will be recalculated, which will involve recalculating the total number of events needed at the final analysis in order to maintain an overall (ie, cumulative over the IA and final analysis) 1-sided Type 1 error $\leq 2.5\%$ and overall power $> 90\%$ when the underlying vaccine efficacy is $\geq 80\%$.

Table 6 Decision Rule and Corresponding Type 1 Error and Power for Testing the Primary Efficacy Hypothesis of VE >0% Against CMVi (3-Dose Regimen vs. Placebo)

| Analysis Time Point | Total Cases to Accrue | Stop for Futility (Vacc Cases) | Case Split for Success (Vacc:Pbo) | VE (95% CI) | Cumulative Type I Error | True Vaccine Efficacy | | | | | |
|---------------------|-----------------------|--------------------------------|-----------------------------------|-------------------|-------------------------|-----------------------|-------|-------|-------|-------|-------|
| | | | | | | 70% | 75% | 80% | 85% | 90% | 95% |
| | | | | | | Cumulative Power | | | | | |
| IA | 15 | ≥7 | ≤3 : ≥12 | 75.0 (7.4, 95.5) | 1.8% | 53.2% | 64.8% | 76.8% | 87.8% | 95.9% | 99.5% |
| Final [†] | 24 | ≥7 | ≤6 : ≥18 | 66.7 (12.3, 89.2) | 2.3% | 73.0% | 83.7% | 92.3% | 97.5% | 99.6% | 100% |

[†] Type I error and power shown are cumulative over the IA and final analysis.
 CI = Confidence interval; IA = Interim analysis; VE = Vaccine efficacy.

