3.1 Statistical Analysis Plan Summary

Key elements of the statistical analysis plan are summarized below; the comprehensive plan is provided in Sections 3.2 to 3.12 of this sSAP. For the purposes of analysis and reporting, the overall study ends when all study efficacy, immunogenicity, and safety data are available and ready for database lock execution.

| | |
|------------------------------|------------------------------------------------------------------------------------------------------------------------------------------------------------------------------------------------------------------------------------------------------------------------------------------------------------------------------------------------------------------------------------------------------------------------------------------------------------------------------------------------------------------------------------------------------------------------------------------------------------------------------------------------------------------------------|
| Study Design Overview | Double-Blind, Randomized, Placebo-Controlled Phase 2b, Multi-center Study to Evaluate the Safety, Tolerability, Efficacy and Immunogenicity of a 2-Dose and a 3-Dose Regimen of V160 (Cytomegalovirus [CMV] Vaccine) in Healthy Seronegative Women, 16 to 35 Years of Age |
| Treatment Assignment | 
Participants will be randomized in a 1:1:1 allocation to one of the following 3 treatment arms:
 
• V160 3-dose regimen: will receive 3 doses of V160 administered IM according to a Day 1, Month 2, Month 6 schedule;• V160 2-dose regimen: will receive 2 doses of V160 administered IM according to a Day 1 (V160), Month 2 (placebo), Month 6 (V160) schedule;• Placebo regimen: will receive 3 doses of saline solution placebo administered IM according to a Day 1, Month 2, Month 6 schedule. 
No stratification based on age, sex or other characteristics will be used in this trial.
 |

| | |

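### The final primary test is run at whatever total of 26 or more cases is counted, although Table 3 shows that some totals, 27 above all, have less power than the total one case earlier or one case later

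*Combined protocol and SAP*

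**What the plan says.** sSAP 3.9.1.1 reports that the interim analysis took place on 17 March 2020 at 17 cases in the 3-dose and placebo arms combined, and that the committee recommended continuing unchanged. If the primary test was inconclusive there, "the final testing of the primary efficacy hypothesis will be conducted when at least 26 total cases of the primary endpoint have been accrued". The section then continues: "In the event of over running the required 26 total cases of the primary endpoint" in those two arms, Table 3 supplies the rule. Table 3 has one row for each final total from 26 to 35, with a limit on vaccine cases, the cumulative one-sided error and the cumulative power. The test is done at the total that happens to be counted. Nothing allows it to be held for another case.

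Protocol 10.9.1.1 sets the standard for an over-run at the interim analysis. It calls for "recalculating the total number of events needed at the final analysis in order to maintain an overall" one-sided error of at most 2.5%, with power above 90% when VE is 80% or more. sSAP 3.6.1 defines success through the lower 95% limit for VE (VE_L above 0%), using person-years in each arm.

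**The concern.** More cases should not make a trial less likely to detect a real effect. Here they can, because the limit is a whole number. From 26 to 27 cases it stays at 7, so the 27th case can only turn a success into a failure. At 28 the limit becomes 8 and power jumps. The same happens at 29, 31, 32 and 34.

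The final primary test is run only if the interim result was inconclusive, and it is then the last chance to show the primary effect. A failure also closes the secondary (2-dose) test under the gatekeeping in sSAP 3.8. Overshoot is a realistic prospect: the interim analysis was planned at 15 cases and done at 17, and Table 3 exists because the sponsor expects the same at the end.

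**Working it through.** **Inputs.** Interim rule at 17 cases: success with at most 3 vaccine cases (sSAP Tables 2 and 3). Final limits: Table 3. Allocation is 1:1 between the two arms. With equal person-time, which the tables imply, a case falls in the vaccine arm with probability p = (1 − VE)/(2 − VE). That is 0.5 at VE 0%, 0.3/1.3 = 0.2308 at VE 70% and 0.2/1.2 = 0.1667 at VE 80%.

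**Formula.** For a final total n with limit c, the cumulative probability of success is P(X17 ≤ 3) + Σ P(X17 = x) × P(Bin(n − 17, p) ≤ c − x), summed over x = 4 to c.

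**Reproducing the plan at 26 cases, limit 7.**
- Error: 0.0064 + 0.0046 + 0.0042 + 0.0018 + 0.0003 = 0.0173 (printed 1.7%).
- Power at VE 70%: 0.4243 + 0.2229×0.8683 + 0.1738×0.6544 + 0.1043×0.3489 + 0.0492×0.0943 = 0.773 (printed 77.3%).

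**The next two totals at VE 70%.**
- 27 cases, limit 7: 0.4243 + 0.1825 + 0.1015 + 0.0303 + 0.0036 = 0.742.
- 28 cases, limit 8: 0.4243 + 0.2037 + 0.1329 + 0.0538 + 0.0118 + 0.0010 = 0.8275.

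The same formula reproduces the error and power entries below to within about 0.1 point. These are the values printed in Table 3:

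| Final total | Vaccine-case limit | Cumulative error | Power, VE 70% | Power, VE 80% |
|---|---|---|---|---|
| 26 | 7 | 1.7% | 77.3% | 94.7% |
| 27 | 7 | 1.3% | 74.2% | 93.7% |
| 28 | 8 | 2.1% | 82.7% | 96.8% |
| 29 | 8 | 1.6% | 80.1% | 96.1% |
| 30 | 9 | 2.4% | 87.1% | 98.1% |
| 31 | 9 | 1.8% | 84.8% | 97.6% |
| 32 | 9 | 1.4% | 82.5% | 97.1% |
| 33 | 10 | 2.1% | 88.6% | 98.6% |
| 34 | 10 | 1.6% | 86.6% | 98.2% |
| 35 | 11 | 2.4% | 91.4% | 99.2% |

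**Gain from waiting one case, at VE 70%.** From 27 to 28: 82.7 − 74.2 = 8.5 points. From 29 to 30: 7.0. From 32 to 33: 6.1. From 34 to 35: 4.8. At VE 80%, 27 to 28 gains 96.8 − 93.7 = 3.1.

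**Why one case of waiting cannot lose a success.** One further case adds at most one vaccine case, and the limit rises by one at each of these steps: 7 to 8, 8 to 9, 9 to 10, 10 to 11. So every success at 27, 29, 32 or 34 is still a success at 28, 30, 33 or 35. Total 31 is different. The next total, 32, is worse, and waiting two cases for 33 could turn 9 vaccine cases into 11 against a limit of 10.

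**The loss where it matters.** Restrict to an inconclusive interim result (4 to 7 vaccine cases of 17): divide the sum over x = 4 to 7 by P(4 ≤ X17 ≤ 7). At VE 70%, the chance of success at the final test is 63.3% at 26 cases, 57.8% at 27 and 73.1% at 28.

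**Sensitivity to person-time.** The documents give no person-time figures, so this is an assumed range. Under VE 0%, p equals the vaccine arm's share of person-time. With the printed limits kept, the error is:

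| Final total, limit | 50% share | 49.5% share | 49% share |
|---|---|---|---|
| 25, limit 7 | 2.37% | 2.66% | 2.97% |
| 26, limit 7 | 1.73% | 1.96% | 2.20% |
| 27, limit 7 | 1.32% | 1.50% | 1.69% |
| 28, limit 8 | 2.07% | 2.34% | 2.64% |

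**The case against.** The plan meets its own standard. Every Table 3 row has error within 2.5% and power above 93% at VE 80%, where protocol 10.9.1.1 asks for more than 90%. The larger gains are at VE 70%, below the value the trial was powered for, so this can be called a preference for optimisation. That stands, and it limits the weight of the point. It does not remove it, because the better rows are already in the plan and cost little to reach.

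Unused error is also not worthless: it protects against unequal person-time. That stands too. Waiting from 27 to 28 spends some of it, and 28 cases with limit 8 would pass 2.5% at a vaccine share of 49%. But the plan already accepts that exposure, since it tests at 28 or 30 if the count lands there.

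Cases are tallied in batches, so waiting from 27 may land on 29 or 31. That stands: one case is the usual wait, not a ceiling, and the guarantee that no success is lost covers only the one-case step.

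A reader might infer that the target should be lowered to 25 cases with the same limit of 7, since at equal person-time 25 succeeds whenever 26 does. The documents do not support that step. Its error of 2.37% holds only at exactly equal person-time and passes 2.5% at a vaccine share of about 49.75%, whereas 26 stays at 2.20% even at 49%. The interim analysis was also run on the plan that the final would be at 26 (Table 3, note c), and lowering a primary case target after an interim look is debatable.

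**Conclusion.** The point holds as a modest loss of efficiency. At 27, 29, 31, 32 and 34 cases the plan tests with less power than at the total just before, and at 27, 29, 32 and 34 one more case would raise the limit. The largest effect is at 27: 8.5 points of cumulative power at VE 70% and 3.1 at VE 80%, compared with 28.

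Two further readings should be avoided. The tests are not invalid: no row exceeds 2.5% under the equal person-time that the tables assume. Nor does every overshoot hurt: 28, 30, 33 and 35 each have more power than 26.

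The figures rest on equal person-time in the two arms, the interim analysis at 17 cases with limit 3, and a waiting decision that depends only on the blinded pooled total.

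**What to change.** Before the next case count, the blinded team should add a sentence to sSAP 3.9.1.1 to this effect: if the pooled total for the final primary test is 27, 29, 32 or 34, the test waits for the next case (28, 30, 33 or 35) and uses the existing Table 3 row; if the next count skips that total, the same rule is applied to the new total. Totals of 26, 28, 30, 31, 33 and 35 are tested as now, the target of 26 is unchanged, and VE_L above 0% with person-time adjustment still governs.

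Costs:
- Usually one more case, more if counts come in batches. As a rough guide, the pooled count went from 6 (22 November 2019) to 17 at the interim analysis (17 March 2020): 11 cases in 116 days, or about 10 to 11 days per case. This treats the interim date as a count date and extrapolates one interval.
- A smaller unused error margin, for example 1.3% to 2.1% from 27 to 28, and at most 2.4% in any row.
- Table 3 ends at 35, so a wait at 34 that skips 35 would have no row. One or two further rows would close this.
- The sponsor should record whether the sentence falls under the amendment clause in sSAP Section 1 for primary methods. It adds no new case limit and can be documented as the version 2.0 changes were.
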